5.2.6.1. Exposure of DSP7888

Dose exposure of DSP7888 will be summarized as below:

- Intended Treatment Duration (weeks) = ((last dose date of DSP7888 + intended timing) OR (last dose of checkpoint inhibitors (CPI) + intended timing) which comes later– (first dose date of DSP7888 or CPI which comes first))/7. Intended timing is 7 days for induction phase, and 14 days for maintenance phase for combination with nivolumab and 21 days for maintenance phase for combination with pembrolizumab.
- Actual Cumulative Dose (mg) = Sum of all administered dose of DSP7888 (mg)
- Actual Dose Intensity (mg/week), ADI = Actual Cumulative Dose (mg) / Intended Treatment Duration (weeks)
- Cumulative Planned Dose = Sum of all protocol-defined planned doses (mg) during the intended treatment duration period
- Planned Dose Intensity (mg/week), PDI = Cumulative planned dose (mg) / Intended Treatment Duration (weeks)
- Relative Dose Intensity (%), RDI = 100 * ADI (mg/week) / PDI (mg/week)

Dose exposure of DSP7888 will also be summarized by phase: Induction Phase and Maintenance Phase.

For the induction phase:

- Intended Treatment Duration (weeks) in the induction phase = (first dose date of DSP7888 in the maintenance phase - first dose date of DSP7888 in the induction phase) / 7 or (last dose date of DSP7888 in the induction phase - first dose date of DSP7888 in the induction phase + 7) / 7 if patients didn't enter the maintenance phase
- Actual Cumulative Dose (mg) in the induction phase = Sum of all administered doses of DSP7888 (mg) in the induction phase
- Actual Dose Intensity (mg/week), ADI in the induction phase = Actual Cumulative Dose (mg) / Intended Treatment Duration (weeks) in the induction phase
- Relative Dose Intensity (%), RDI in the induction phase = 100 * ADI (mg/week) / Planned Dose Intensity (Table 11)

For the maintenance phase:

- Intended Treatment Duration (weeks) in the maintenance phase = (last dose date of DSP7888 in the maintenance phase - first dose date of DSP7888 in the maintenance phase + intended timing) / 7. Intended timing is 14 days in combination with nivolumab and 21 days in combination with pembrolizumab.
- Actual Cumulative Dose (mg) in the maintenance phase = Sum of all administered doses of DSP7888 (mg) in the maintenance phase
- Actual Dose Intensity (mg/week), ADI in the maintenance phase = Actual Cumulative Dose (mg) / Intended Treatment Duration (weeks) in the maintenance phase
- Relative Dose Intensity (%), RDI in the maintenance phase = 100 * ADI (mg/week) / Planned Dose Intensity (Table 11)

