### **Phase 1b**

After providing written informed consent, patients will undergo screening assessments, which will include a careful review of each patient's medical history.

Patients will be administered doses of DSP-7888 Dosing Emulsion intradermally in both arms of the study (Arm 1 and Arm 2). Arm 1 will include patients with indications approved by the Health Authorities for treatment with nivolumab: advanced melanoma, non-small cell lung cancer (NSCLC), RCC, urothelial carcinoma, head and neck squamous cell carcinoma (HNSCC), hepatocellular carcinoma (HCC), and microsatellite instability-high or mismatch repair-deficient (MSI-H/dMMR) colorectal cancer. Arm 2 will include patients with indications approved by the Health Authorities for treatment with pembrolizumab: melanoma, NSCLC, HNSCC, urothelial carcinoma, MSI-H/dMMR cancer, gastric cancer or gastroesophageal junction adenocarcinoma, and cervical cancer.

In the Phase 1b dose search part of the study, during the Arm 1 induction phase (4 weeks), DSP-7888 Dosing Emulsion will be administered once weekly for 4 weeks, with nivolumab administered every other week. In the subsequent Arm 1 maintenance phase, DSP-7888 Dosing Emulsion will be administered once every 2 weeks with nivolumab until a discontinuation criterion is met. During the Arm 2 induction phase (6 weeks), DSP-7888 Dosing Emulsion will be administered once weekly for 6 weeks, with pembrolizumab administered once every 3 weeks. In the subsequent Arm 2 maintenance phase, DSP-7888 Dosing Emulsion will be administered once every 3 weeks with pembrolizumab until a discontinuation criterion is met.

Both programmed cell death-1 (PD-1) inhibitors (nivolumab and pembrolizumab) will be administered in the approved dose and schedule starting on Day 1 of the study. Study sites will not be limited to any arm of the study, and each arm will investigate the recommended dose in parallel.

Objective disease assessments will be performed according to RECIST (v1.1) and iRECIST, with the first assessment performed at the end of the dose-limiting toxicity (DLT) period (Cycle 3: at 4 weeks for nivolumab arm, at 6 weeks for pembrolizumab arm), and at Weeks 12, 18, and 24 after the first dose of DSP-7888 Dosing Emulsion. After that, objective disease assessments will occur every 12 weeks until patient discontinuation from the study.

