### **8.3. Dose Modification**

Any study treatment may be interrupted at any time for any grade toxicity considered intolerable by the patient, based on the investigator's and patient's judgment.

In the case of any patient who has missed 4 or more consecutive doses of either study drug, that study drug should be permanently discontinued, but the patient may continue on the other nonmissed study drug. If the patient is experiencing clinical benefit and, in the opinion of the investigator it is in the patient's best interest to remain on study, the patient may continue treatment on a case-by-case basis, after documented discussion with the Sponsor.

Dose modification by treatment is described in the following sections.

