5.2.6. Extent of Exposure

Dose Schedule for phase 1b part is summarized as below:

Table 5: Phase 1b Study Dose Level and Schedule

DSP-7888 Dosing Emulsion Dose Level	DSP-7888 Dosing Emulsion Dose and Schedule
DSP-7888 Dosing Emulsion Dose Level I	Nivolumab Arm (Arm 1): 10.5 mg weekly for 4 weeks for induction phase, then every 2 weeks for maintenance phase Pembrolizumab Arm (Arm 2): 10.5 mg weekly for 3 weeks for induction phase, then every 3 weeks for maintenance phase
DSP-7888 Dosing Emulsion Dose Level II	Nivolumab Arm (Arm 1): 3.5 mg weekly for 4 weeks for induction phase, then every 2 weeks for maintenance phase Pembrolizumab Arm (Arm 2): 3.5 mg weekly for 3 weeks for induction phase, then every 3 weeks for maintenance phase
DSP-7888 Dosing Emulsion Dose Level III	Nivolumab Arm (Arm 1): 1.75 mg weekly for 4 weeks for induction phase, then every 2 weeks for maintenance phase Pembrolizumab Arm (Arm 2): 1.75 mg weekly for 3 weeks for induction phase, then every 3 weeks for maintenance phase

Table 6: PD-1 Inhibitor Dose

PD1 Inhibitor	Dose and Schedule
Nivolumab	In Arm 1, 240 mg administered intravenously (IV) over 30 minutes (± 5)* every 14 days (2 weeks/cycle) starting from Day 1 of Cycle 3 (Day 29), then maintenance phase (after Cycle 3).
Pembrolizumab	In Arm 2, 200 mg/8 mL administered through IV infusion over 30 (± 5) minutes every 21 days (3 weeks) starting from Day 1 of Cycle 2 (Day 22), then maintenance phase (after Cycle 2).

*The administration time change from 60 to 30 minutes is based on the updated dosage and administration guidance of the new nivolumab product label released in July 2018.

DSP-7888 Dosing Emulsion and pembrolizumab will be administered at the recommended dose level from the Phase 1 part of the study, following the same schedule as listed in Table 10.

Table 7: Phase 2 Study Dosing Schedule

Investigational Product	Frequency	Dosage	Route of Administration
DSP-7888 Dosing Emulsion	Q1W for first 3 weeks Q3W post 3 weeks	10.5mg	Intradermal injection (ID)
Pembrolizumab	Q3W, starting from Day 1 of Cycle 2 (Day 22)	Solution for infusion 200mg/8mL	IV infusion

The dose schedules for the study have been changed under different protocol amendment. Below is a summary of the different dosing schedule:

Table 8: Planned Dose Intensity

Treatment Group	Dose Level	During Induction Phase	During Maintenance Phase
DSP-7888 Dosing Emulsion + nivolumab	Level I (10.5 mg)	10.5 mg / week	5.25 mg / week

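### By-phase DSP-7888 dose intensity splits at the first maintenance dose actually given, so missed leading maintenance doses lower induction RDI and drop out of maintenance RDI

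*SAP*

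**What the plan says.** SAP Section 5.2.6.1 defines an overall DSP-7888 RDI and then a separate summary for induction and for maintenance. By phase, the durations in weeks are:

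- Induction, patient enters maintenance: "first dose date of DSP7888 in the maintenance phase - first dose date of DSP7888 in the induction phase) / 7".
- Induction, patient does not enter maintenance: "last dose date of DSP7888 in the induction phase - first dose date of DSP7888 in the induction phase + 7) / 7".
- Maintenance: "last dose date of DSP7888 in the maintenance phase - first dose date of DSP7888 in the maintenance phase + intended timing) / 7". The interval added at the end depends on the partner drug: "Intended timing is 14 days in combination with nivolumab and 21 days in combination with pembrolizumab".

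The dates in the first and third formulas are dates of doses, with no reference to the schedule. The plain reading is therefore the dose actually given. By-phase RDI is the actual mg per week divided by the planned mg per week for that phase. The text cites Table 11 for the planned values, but they stand in SAP Table 8.

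Dose intensity is one of the Phase 1b primary endpoints (SAP Section 1.2.1, Table 1). Version 3.0 of the SAP restricts the final report to safety, so exposure is among the analyses that remain.

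**The concern.** The two durations share one boundary, and that boundary moves with the patient's behaviour. If the first scheduled maintenance dose is missed or held, the weeks until dosing resumes enter the induction denominator and never enter the maintenance one. Patients with identical induction dosing then receive different induction RDI, and the one who resumes treatment scores lower than the one who stops.

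The situation can arise within the protocol. Sections 8.3.1 and 8.3.2.2 provide for holding DSP-7888 for related Grade 3 or 4 toxicity. Section 8.3 calls for permanent discontinuation only once a patient has "missed 4 or more consecutive doses of either study drug", so one to three missed doses followed by resumption is foreseen. What is at stake is whether the by-phase exposure table shows correctly in which phase doses were lost.

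**Working it through.** **Inputs.** Schedules, from SAP Section 5.2.6 (Table 5 and Figure 1) and the protocol synopsis:

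- Nivolumab: "10.5 mg weekly for 4 weeks for induction phase, then every 2 weeks for maintenance phase"; first planned maintenance dose Day 29.
- Staggered pembrolizumab (Phase 1b enrichment, and Phase 2 from Amendment 5): "10.5 mg weekly for 3 weeks for induction phase, then every 3 weeks for maintenance phase"; first planned maintenance dose Day 22.
- Legacy pembrolizumab: "DSP-7888 Dosing Emulsion will be administered once weekly for 6 weeks, with pembrolizumab administered once every 3 weeks"; first planned maintenance dose Day 43, then every 3 weeks.

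**Table 8 reproduced (Level I).** Dose divided by interval: 10.5/1 = 10.5 mg/week in induction; 10.5/2 = 5.25 (nivolumab) and 10.5/3 = 3.5 (pembrolizumab) in maintenance. These match. A patient exactly on schedule gets 100% in both phases on all three schedules.

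**Scenario.** All induction doses are on time, the first k maintenance doses are missed, and four further doses follow on time. Every dose is 10.5 mg.

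Worked case, staggered pembrolizumab, k = 1: doses on Days 1, 8, 15, then 43, 64, 85, 106.

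- Induction: (43 − 1)/7 = 6 weeks; 31.5 mg/6 = 5.25 mg/week; 5.25/10.5 = 50%.
- Maintenance: (106 − 43 + 21)/7 = 12 weeks; 42 mg/12 = 3.5 mg/week; 3.5/3.5 = 100%.
- Maintenance doses given against planned: 4/5 = 80%.
- Overall: 7 of 8 planned doses = 87.5%.

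| Schedule | k | First maintenance dose | Induction weeks | Induction RDI | Maintenance RDI | Planned maintenance doses given | Overall RDI |
|---|---|---|---|---|---|---|---|
| Staggered pembrolizumab | 1 | Day 43 | 6 | 50.0% | 100% | 80.0% | 87.5% |
| | 2 | Day 64 | 9 | 33.3% | 100% | 66.7% | 77.8% |
| | 3 | Day 85 | 12 | 25.0% | 100% | 57.1% | 70.0% |
| Nivolumab | 1 | Day 43 | 6 | 66.7% | 100% | 80.0% | 88.9% |
| | 2 | Day 57 | 8 | 50.0% | 100% | 66.7% | 80.0% |
| | 3 | Day 71 | 10 | 40.0% | 100% | 57.1% | 72.7% |
| Legacy pembrolizumab | 1 | Day 64 | 9 | 66.7% | 100% | 80.0% | 90.9% |
| | 2 | Day 85 | 12 | 50.0% | 100% | 66.7% | 83.3% |
| | 3 | Day 106 | 15 | 40.0% | 100% | 57.1% | 76.9% |

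**Same induction, no maintenance dose (staggered).** (15 − 1 + 7)/7 = 3 weeks; 31.5/3 = 10.5 mg/week; 100%.

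**Smaller departures.** A first maintenance dose 2 days late, with no dose missed, gives induction RDI of 21/23 = 91.3% (staggered), 28/30 = 93.3% (nivolumab) or 42/44 = 95.5% (legacy). One dose missed between four given maintenance doses is detected: maintenance RDI is 4/5 = 80%.

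**The case against.** The strongest points on the other side are these.

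- **The headline measure is sound.** Overall RDI compares administered with all planned doses and falls as it should. SAP Section 5.2.6 also counts patients with a reduction or interruption, and Section 5.4.1 tabulates adverse events leading to either. This stands, and it limits the point to the by-phase rows.
- **Nothing is decided on these rows.** The recommended dose rests on DLT counts and overall tolerability (Protocol Section 6.5, SAP Section 5.3), and the dose search is complete. This stands too.
- **Charging the delay to induction is defensible**, because toxicity present at the first maintenance visit follows induction dosing. As attribution this can be argued, but the formula does not deliver it. The added weeks are charged at 10.5 mg/week when the schedule planned one 10.5 mg dose in them. Charging one missed dose to a three-dose induction would give 3/4 = 75%, not 50%.
- **The current boundary does something useful.** With Day 15 missed and maintenance starting on Day 22 on time, the SAP gives induction 21 mg/3 weeks = 7 mg/week, or 66.7%, which is right. A reader might infer that the formula for patients who never enter maintenance should simply be used for everyone. It should not: in this case induction would read 21 mg/2 weeks = 100%, and maintenance, started on Day 15 with four doses to Day 85, would read 42 mg/13 weeks = 3.23 mg/week, or 92.3%. Both are wrong. Missed induction doses are plausible, since the dose-determining set (Protocol Section 12.1.2.3) accepts patients with half the planned doses.

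**Conclusion.** The point holds for the by-phase summaries. For a complete, on-time induction followed by one to three missed leading maintenance doses and resumption, induction RDI is understated at 25% to 67%, and maintenance RDI reads 100% where 57% to 80% of planned doses were given.

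These sizes assume that dose dates mean doses actually given, that four maintenance doses follow on time, and that dosing resumes at 10.5 mg; the induction values depend only on the first of these. The lower limit of 25% takes three as the most consecutive doses missed. Section 8.3 allows case-by-case continuation beyond that, and four missed doses would give 20% (staggered) or 33% (the other two schedules).

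A reader might infer that the Phase 1b dose-intensity endpoint as a whole, or the recommended dose, is compromised. The documents do not support that: the endpoint is stated without a phase split, overall RDI is unaffected, and no rule uses the by-phase values. Nor do they show how many patients are affected. Small groups make single patients visible, however. Protocol Section 4.3.2 reports six patients in the pembrolizumab dose-search arm; if they were summarised alone, one patient at 40% and five at 100% would give a mean induction RDI of 540/6 = 90%. The correction is worth making, at modest priority.

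**What to change.** For patients who enter maintenance, define one phase boundary: the later of (a) last induction dose plus 7 days and (b) the scheduled first maintenance date under the patient's own schedule, but no later than the actual first maintenance dose. The scheduled date is Day 29 for nivolumab, Day 22 for staggered pembrolizumab including Phase 2 from Amendment 5, and Day 43 for legacy pembrolizumab, which Protocol Section 6.1.4 also applies to Phase 2 patients enrolled under Amendment 4. End the induction duration and start the maintenance duration at that boundary. Keep the existing formula for patients who never enter maintenance.

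Check on both cases:

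- Worked case (Day 22 missed): boundary Day 22; induction 31.5 mg/3 weeks = 100%; maintenance (106 − 22 + 21)/7 = 15 weeks, 42/15 = 2.8 mg/week, 80%.
- Day 15 missed, Day 22 given: boundary Day 22; induction stays at 66.7%, maintenance at 100%.

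The cost is two formula edits in Section 5.2.6.1 and the matching program lines, using dose dates already collected and the schedules in SAP Figure 1. Maintenance RDI will fall for affected patients, for example from 100% to 80%, 67% or 57% in the scenarios above. The Table 11 reference can be corrected to Table 8 in the same edit.

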5.2.6.2. Exposure of Nivolumab

Nivolumab is planned to provide as 240 mg administered intravenously (IV) over 30 minutes (± 5) every 14 days (2 weeks/cycle). The exposure of nivolumab is summarized as below:

- Intended Treatment Duration (weeks) = (last dose date of nivolumab – first dose date of nivolumab + 14 days) / 7.
- Actual Cumulative Dose (mg) = Sum of all administered dose of nivolumab
- Actual Dose Intensity (mg/week), ADI = Actual Cumulative Dose (mg) / Intended Treatment Duration (weeks)
- Relative Dose Intensity (%), RDI = 100 * ADI (mg/week) / (120 mg / week)

5.2.6.3. Exposure of Pembrolizumab

Pembrolizumab is provided as 200 mg/8 mL administered through IV infusion over 30 (± 5) minutes every 21 days. The exposure of pembrolizumab is summarized as below:

- Intended Treatment Duration (weeks) = (last dose date of pembrolizumab – first dose date of pembrolizumab + 21 days) / 7.
- Actual Cumulative Dose (mg) = Sum of all administered dose of pembrolizumab

- Actual Dose Intensity (mg/week), $ADI = \text{Actual Cumulative Dose (mg)} / \text{Intended Treatment Duration (weeks)}$
- Relative Dose Intensity (%), $RDI = 100 * ADI \text{ (mg/week)} / (200 / 3 \text{ (mg / week)})$

5.3. Statistical Methodology

Phase 1b

Determination of Recommended Dose of DSP-7888 Dosing Emulsion with nivolumab or pembrolizumab (Only Phase 1b)

Determination of a recommended dose of DSP-7888 Dosing Emulsion in combination with nivolumab or pembrolizumab will be based on the criteria defined herein.

Initially, 6 patients will be enrolled into each of the Arms according to a rolling 6 study design at the DSP-7888 Dosing Emulsion Dose Level I of 10.5 mg weekly, in combination with either nivolumab 240 mg (every 2 weeks; Arm 1) or pembrolizumab 200 mg (every 3 weeks; Arm 2).

The recommended dose of DSP-7888 Dosing Emulsion in combination with a given PD-1 inhibitor agent will be determined in each study Arm. Dose adjustments will proceed independently in each study Arm. The recommended dose of DSP-7888 Dosing Emulsion must be less than or equal to a dose level at which 1 out of 6 patients enrolled experience a DLT (see definition of a DLT in Section 7.4 of protocol). A dose level is eligible for consideration as the recommended dose if 0 or 1 of 6 patients enrolled experience a DLT at that dose level.

Criteria for determining whether a given dose level is eligible to be considered a recommended dose of DSP-7888 Dosing Emulsion are based on the number of patients with DLTs out of the total number of DLT-eligible patients in a given cohort. The criteria are as specified below:

- If 0 or 1 out of 6 patients at the starting dose level experience a DLT, then the dose level is eligible for consideration as the recommended dose of DSP-7888.
- If 2 or more out of 6 patients at a given dose level experience a DLT, then the dose will be decreased. Further enrollment will be made at the lower dose level. If 0 or 1 out of 6 patients at the lower dose level experience a DLT, then the dose level is eligible for consideration as the recommended dose of DSP-7888.

The determination of the recommended dose of DSP-7888 Dosing Emulsion in a given study Arm also will be based on overall tolerability, including a review of persistent Grade 2 AEs and a review of AEs occurring beyond the first 2 dosing cycles.

Phase 2

A Bayesian decision making framework will be employed to quantify whether proof of concept (POC) can be established based on the overall response rate (ORR) by Week 24 from the final analysis for the overall population and/or the CPS < 10 subpopulation. The POC is established at the final analysis if either or both of the following 2 conditions are met:

- In the overall population, 70% credible interval of ORR with 10% in the left tail and 20% in the right tail will be calculated: if lower bound $\geq 8\%$ and upper bound $\geq 21\%$ (where 8% is the reference value [Section 4.3.1] and 21% is the target value of ORR in the overall population), the study will achieve POC.
- In the CPS < 10 subpopulation, 50% credible interval of ORR with 20% in the left tail and 30% in the right tail will be calculated: if lower bound $\geq 5\%$ and upper bound $\geq 15\%$ (where 5% is the reference

value [Section 4.3.1] and 15% is the target value of ORR in CPS < 10 subpopulation), the study will achieve POC.

The interim monitoring analysis for futility or early efficacy assessment will be conducted using a Bayesian method and will start after the first 20 patients have response evaluation, withdraw, or die by Week 24.

- If the posterior probability of $ORR \geq 21\%$ in the overall population is $\leq 2.5\%$ AND the posterior probability of $ORR \geq 15\%$ in the CPS < 10 subpopulation is $\leq 2.5\%$, the study is futile and further enrollment will be stopped.
- If the posterior probability of $ORR \geq 21\%$ in overall population is $\geq 80\%$ AND the posterior probability of $ORR \geq 15\%$ in CPS < 10 subpopulation is $\geq 70\%$, then early success is met and further enrollment may be stopped.
- Otherwise, the enrollment will continue until 40 evaluable patients have been accrued.

The above decision rules for interim analysis are non-binding.

5.4. Safety Analyses

The safety and tolerability of DSP-7888 Dosing Emulsion in combination with immunotherapy PD-1 inhibitors will be assessed for the duration of study treatment until 30 days after last dose date.

5.4.1. Adverse Events

Treatment-Emergent Adverse Events

An AE will be regarded as treatment-emergent, if

- it occurs for the first time on or after the first dose date of either DSP-7888 or CPI up to 30 days after the last dose of study drug; or
- it occurs up to any time if serious and considered related to study drug.

The emphasis for AE analysis will be based on treatment-emergent AE (TEAE), however all AEs will be listed.

All AEs will be coded using Medical Dictionary for Regulatory Activities (MedDRA version 20.0) and summarized by MedDRA System Organ Class and Preferred Term. The severity of all AEs will be graded by the Investigator using NCI CTCAE version 4.0.

An overview of treatment-emergent adverse events (TEAEs) will be provided. The number and percentage of subjects with following will be summarized for phase 1b, Arm 1 and Arm2 overall, phase 2: CPS < 10, CPS \geq 10 and Overall.

- Subjects with any TEAE
- Subjects with TEAE of CTCAE grade 3 or higher
- Subjects with serious adverse events (all causality and related)
- TEAEs related to study drug
- TEAEs related to study drug with CTCAE grade 3 or higher
- Subjects with TEAE leading to study drug discontinuation (all causality and related)
- Subjects with TEAE leading to study drug dose reduction (all causality and related)
- Subjects with TEAE leading to study drug dose interruption (all causality and related)

Summary of AEs by SOC and Preferred Term

The number and percentage of subjects with TEAEs by SOC, PT and maximum CTCAE grade will be summarized. A summary of TEAEs of CTCAE grade 3 or higher (Grade 3, 4, 5) will be presented by SOC and PT and maximum CTCAE grade (All Grade, \geq Grade 3).

The number and percentage of patients who experience any TEAE will be summarized by SOC and PT (All Grade, \geq Grade 3). A summary of TEAEs by PT and maximum CTCAE grade will be presented. The most commonly reported TEAEs using a different cutoff (e.g. 2% or 10% or more of patients in either arm) may also be summarized by PT as needed.

TEAEs associated with permanent discontinuation /dose reduction/drug interruption of either DSP7888 and/or CPI will be summarized by SOC and PT and maximum CTCAE Grade (taking into consideration the action taken from CRF AE page).

Treatment Related Adverse Events

Treatment-related TEAEs are those judged by the investigator to be at least possibly related to the study drugs (DSP7888 and/or CPI) or for which relatedness is recorded as “unknown” by the investigator. Treatment related will include “possible”, “probable” or “definite” causality assessments. Missing relationship will be considered as “Related” to all drugs received by the patient. Similar summaries as noted for all causality TEAEs will be provided for treatment related TEAEs.

Serious Adverse Events and Death

Treatment-emergent SAEs and Treatment-related SAEs will be summarized by MedDRA SOC and PT and maximum CTCAE grade.

TEAE leading to death will be summarized by MedDRA SOC and Preferred Term.

Deaths will be summarized by on study and on treatment (within 30 days of last dose of study medication). The number and percentage of patients who died on study and on treatment, as well as primary cause of death will be summarized. Deaths may also be categorized according to time of occurrence after first dose.

A listing of death data will also be provided and will include all deaths that occurred from the signing of the informed consent to the end of the follow up period. The listing will include primary cause of death and the number of days relative to the administration of first and last dose.

Adverse Events of COVID-19

Preferred Terms corona virus infection and coronavirus test positive will be used to identified COVID-19 positive cases in adverse event.

Injection Site Reaction (ISR)

The predominant adverse effect observed with DSP-7888 is injection site reaction. The Preferred Terms of TEAEs within the High Level Group Term of “Administration Site Reaction” (MedDRA version 20.0) will be used to identify events of injection site reaction.

Below analysis will be provided for ISR:

- ISR by SOC, PT, and maximum CTCAE Grade
- Onset time of first ISR for patients with at least one ISR: Time to onset is analyzed for patients with at least one ISR from the first dose of the DSP-7888 to the first occurrence of ISR regardless of CTCAE grade.
- Onset time of first ISR: Time to first ISR is defined as the time from the first dose of the DSP-7888 to the first occurrence of ISR . For patients with no ISR, the onset time will be censored as data cutoff date,

end of study date, death date, or safety follow-up completion date (end of treatment date + 30 days) whichever is shorter.

- Onset time of the first Grade 3 or higher ISR for patients with at least one Grade 3 or higher ISR: Time to onset is analyzed for patients with at least one Grade 3 or higher ISR from the first dose of DSP-7888 to the first occurrence of the Grade 3 or higher ISR.
- Onset time of the first Grade 3 or higher ISR: Time to first Grade 3 or higher ISR is defined as the time from the first dose of DSP-7888 to the first occurrence of the Grade 3 or higher ISR. For patients with no Grade 3 or higher ISR, the onset time will be censored as data cutoff date, end of study date, death date, or safety follow-up completion date (end of treatment date + 30 days) whichever is shorter.
- Duration of ISR and Duration of Grade 3 or higher ISR and may be analyzed in the CSR. The duration is defined as (end date – start date + 1), and for ongoing ISR/ or ongoing Grade 3 or higher ISR, the ISR end date is truncated as the minimum of {by data cutoff date, end of study date, death date, last known to be alive date, or safety follow-up completion date (end of treatment date + 30 days)} whichever is shorter.

A listing of ISR will also be provided.

